## **I. Overview**

The triple threat of rural geography, racial inequities, and older age hinders access to high quality palliative care (PC) for a significant proportion of Americans. Rural patients with life-limiting illness are at very high risk of not receiving appropriate care due to a lack of health professionals, long distances to treatment centers, and limited PC clinical expertise. Although culture strongly influences people's response to diagnosis, illness and treatment preferences, culturally-based care models are not currently available for most seriously-ill rural patients and their family caregivers. Lack of sensitivity to cultural differences may compromise PC for minority patients.

The two major public health consequences of these problems are:

- 1) Access-Rural patients have sub-optimal or no access to PC. Despite significant nationwide growth, access to PC is grossly inadequate for the 60 million US citizens who live in rural or non-metropolitan areas. There is low PC use in rural and minority populations. As a result, rural patients experience significant suffering from uncontrolled symptoms that PC expertise could alleviate.
- 2) Acceptability-Even when palliative and hospice services are available, African Americans (AA), compared to Whites (W) are more likely to receive medically-ineffective, poor quality care due to a culturally-insensitive health care system and mistrust of health care providers. Making culturally competent PC available for diverse underserved and rural Americans is a national priority.

Our community-developed, culturally based tele-consult intervention, specifically targets the gaps of PC access and acceptability. It was developed by and for rural, Deep South AA and W patients and providers, and uses state-of-the-art telehealth methods, to provide PC consultation to hospitalized seriously-ill patients and family. Using National Consensus Project guidelines, and the culturally-based, community-developed PC Tele-consult intervention, a remote PC expert conducts a comprehensive PC patient assessment, in collaboration with local providers. Following interdisciplinary PC team review, the remote clinician communicates recommendations. Two additional structured follow up contacts at Day 3 and 6 ensure care coordination and smooth transitions that enable patients to receive guideline concurrent PC in their communities.

Almost three decades after the Institute of Medicine's landmark report, "Approaching Death" their revised report, "Dying in America," continued to document that hospitalized patients with serious illness are experiencing unnecessary suffering from uncontrolled symptoms. This occurs disproportionately in rural and minority citizens, especially those in the Deep South. Our study will move the field forward by testing a promising culturally-based tele-consult intervention that is scalable, and was developed by and for the community it will serve.

## **II. Aims of the Study**

The aims of this study are to compare a robust, culturally-based tele-consult program to usual hospital care to:

- a. Primary Aim:** Determine whether a culturally-based PC tele-consult program leads to lower symptom burden in hospitalized AA and W older adults with a life-limiting illness.
- b. Secondary Aim:** Determine whether a culturally-based PC tele-consult program results in higher patient and caregiver quality of life, care satisfaction, and lower caregiver burden at Day 7 post-consultation, and lower resource use (hospital readmission, emergency visits) 30-days post-discharge
- c. Exploratory Aim:** Explore mediators and moderators of patient symptom and caregiver burden outcomes.

[figure not shown]

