#### IV. Study Design

This study consists of 2 phases:

**Phase I Convening & Soliciting CAG Participation in study design.** This phase will consist of assembling CAG members to review study procedures and some CAG members will be trained to approach potential study participants. Potential CAG members (8, with equal numbers of AA and W) will be identified by the hospital staff and community leaders of each of the three sites, and invited to participate in the CAG. Potential CAG members will include respected members of the community, those who have recently lost a loved one and understand end of life care, and community leaders. Potential members will be discussed by the recruiters with the study PIs to ensure there is socio-demographic balance, and equal representation of African American and

White members, to ensure all will feel comfortable participating and contributing, and to ensure that they are not all from the same family/church/social group. Following this step, a formal written invitation will be extended to those selected, followed by a phone call by the Study Manager.

**Phase II Conducting the RCT.** In Phase II, we will conduct a randomized controlled trial (RCT) at the 3 sites to test the effectiveness of this innovative program. We will recruit 352 hospitalized AA and W adults over age 65 whose treating physician would not be surprised if they died within the next year and the patients' family/friend caregiver. Half of the patient participants (N=176) will be randomized to receive usual care appropriate to their illness. Patients randomized to usual care in each of the three participating hospitals will receive inpatient care appropriate to their illness. This includes assessment and treatment by the admitting physician, along with any subspecialists that are consulted. The formulation and sharing of prognostic information and the engagement of patients and families in establishing goals of care will be according to the standards of the admitting physician and subspecialists. Treating clinicians may include hospitalists, nurse practitioners, social workers, pastoral care, and occasionally, the patient's primary care practitioners who have hospital privileges.

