### **Consent Process:**

**a. Approaching the patient and family:** The CSC will screen admissions each weekday and will only approach potential study participants after confirming eligibility (e.g. “surprise question”) and getting approval from the treating clinician.

**b. CAG and CSC meet with patient and family:** Following approval, the CSC will contact the CAG member “on-call” for the day to speak with the patient. The CAG member and CSC will approach the patient. The CAG member will introduce themselves and the CSC, and describe the study to the patient. The CAG will emphasize their role in developing the study and how this study was designed to help the community. If the patient indicates that he/she would like to participate, the CSC will provide an overview of the study, including a description of palliative care, the tele-consult equipment and process, (if randomized to that group), and randomization using a simple visual diagram. (These materials were developed by the R21 CAG and will be reviewed and adapted by each hospital-specific CAG). The CSC will then read the consent form to all patients (assuming no or limited literacy) unless the patient prefers to read it themselves. The family member is invited to participate and will sign a separate consent agreeing to complete questionnaires regardless of group assignment. The CSC will assist the patient (and separately the family member) to complete the baseline questionnaires using an electronic tablet that connects directly to the REDCap database. Baseline data are collected prior to randomization, so study coordinator blinding is not necessary.

The CSC will screen, obtain consent and organize the tele-consult. The CSCs will remain in daily contact with hospital staff and participate in team meetings to remind clinicians about eligibility criteria. Team meeting attendance will allow the CSC to clarify the study goals and protocol and to strategize solutions if challenges arise. The BSC will collect all data following patient randomization.

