Within 24 hours of conducting the Tele-consult, the remote palliative physician will seek an interdisciplinary team review, develop the plan, and make recommendations, which may include immediate patient care (e.g., symptom relief) and continuing care, related to the hospital stay and following discharge. Recommendations may also include referrals to other supportive resources such as a hospital social worker or pastor. The written consult will be documented using a standardized note template that corresponds to the 8 NCP palliative care domains and will be provided via a secure HIPAA-compliant portal that will be part of the patients' inpatient medical record. As needed, verbal contact will also occur between the palliative care physician and the hospitalist staff.

**Contact #2** Day 3 (approximately 24-48 hours after first contact). The CSC will arrange a follow up videoconference between the remote palliative care physician and patient if in hospital or via phone if the patient has been discharged. The purpose of this second contact is to determine how patient is progressing, if the plan was implemented, if hospital staff/patient has encountered any challenges or questions, and to determine who will be assuming the patient's care in the community. Documentation of the contact will be provided as described above.

**Contact #3** Day 6 (post consult) (via videoconference if patient is in hospital, via phone if discharged.) To determine if patient is experiencing new or ongoing challenges, to confirm availability of community or hospice care as appropriate.

**Tele-consult Intervention + Usual Care.** In the usual care group and the intervention group, a study coordinator at each site will administer questionnaires to the patient and their designated family/friend caregiver, in person or telephone (if patients are discharged during the study period) at baseline (T1), Day 7 (T2) and Day 30 after hospital discharge (T3). (Study coordinators administering T2/T3 assessments will be blinded to study group- aka Blinded Study Coordinators [BSC]).

Table 5. Measures and Data Collection Schedule						
Construct	Instrument & Description	# of Items	T1 Baseline	T2 Day 7	T3 Day 30	
Demographics	Demographic Questionnaire- Age, gender, race/ethnicity, marital status, religion, education, occupation, insurance status, financial status.	10	X			
Primary Aim						
Symptom Burden	Edmonton Symptom Assessment Scale (ESAS) - symptom intensity using visual analog	9	X	X		

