Secondary Aims						
Patient and Caregiver QoL	PROMIS Global Health -10. Evaluates physical, social, and emotional health in healthy & chronically ill adults	10	X	X		
Family Satisfaction with Care	FamCare - family satisfaction with availability of care, physical & psychosocial care, information giving	20	X	X		
Patient Satisfaction with Care	Feeling Heard and Understood - Self-report quality measures for palliative care settings on Likert scale (1 item)	1	X	X		
Caregiver Burden	Montgomery Borgatta Caregiver Burden Scale (MBCB)-subscales objective, subjective, demand burden	14	X	X		
Resource Use	Hospital admission, ED visit, hospice	NA			X	
Exploratory Aim						
Mediators	Consult recommendations implemented by Hospitalist & Pt	NA		X		

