## **XII. Data Management Plan**

Study coordinators will securely manage all data and PHI in accordance with HIPAA and IRB regulations, and maintain data confidentiality and anonymity. The only physical study document that will contain identifiable information will be the informed consent document, which the study coordinator will store in a secure, locked location until it can be securely transferred to a locked cabinet at the University of Alabama at Birmingham (UAB). All other study documents will only contain the patient's UID, but no identifiers.

The CSC and BSC will transmit all study documents to [name], the study statistician, for data analysis. This includes questionnaires, fidelity checklists, data collection sheets, spreadsheets, and any other data collection instruments and tools.

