### **a. Spreadsheets**

Each CSC and BSC will maintain a number of spreadsheets and documents to track all aspects of data collection at their respective sites.

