**c. Data collection sheet**

The CSC will fill out a data collection sheet for each patient (both Group A and Group B), using patient's UID. The data collection sheet will record:

- Demographics
- Diagnosis
- Readmissions
- Study group
- PC recommendations
- Family implementation of PC recommendations (determined via family interview)

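### Does 30-day resource use need a written denominator, a death rule and named date fields before the plan is sound?

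*Combined protocol and SAP*

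**What the plan says.** Section II (Secondary Aim) names "lower resource use (hospital readmission, emergency visits) 30-days post-discharge". The Resource Use row of Table 5 in Section X lists "Hospital admission, ED visit, hospice", collected at T3 only. Section X times T3 at 30 days from hospital discharge and has a study coordinator question both the patient and the designated caregiver, in person or by telephone.

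The population in Section IV is patients "whose treating physician would not be surprised if they died within the next year". Section VI requires each patient to have an involved caregiver and excludes those without one.

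Section XI (Statistical Analysis Plan) covers baseline comparisons, covariate choice and tabulation by arm. It mentions regression models but sets none out, and it does not discuss resource use.

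Section XII describes a referral spreadsheet, a linkage log, a recommendations spreadsheet, a fidelity checklist, a data collection sheet and questionnaires. The list that follows "The data collection sheet will record" includes readmissions, but not emergency visits, discharge date or death. The same section says that coordinators keep documents to "track all aspects of data collection at their respective sites", and that the statistician also receives "any other data collection instruments and tools".

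**The concern.** In a seriously ill population some patients will die in hospital or within 30 days of leaving it, and a patient who has died can no longer be readmitted. If one arm had more deaths, it would show fewer readmissions for that reason alone, and this could be read as lower resource use. The reported percentage also depends on whether the base is everyone randomised, those discharged alive or those alive at Day 30. With no rule written down, that choice could be made after the data are seen. If death and discharge dates were never captured, nobody could later separate less use from less time at risk.

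**Working it through.** **What the plan gives.** It states no readmission rate, mortality rate, power or effect size for resource use, so there is no figure to reproduce. The only usable input is 176 patients per arm (Section IV; 176 + 176 = 352). Every rate below is an assumption.

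**Assumptions.** There is no true effect on readmission. A share b = 25% or 30% would be readmitted within 30 days if nobody died. Deaths are d = 5% in one arm and 10% in the other.

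**Deaths after discharge, independent constant hazards.** Take the 30-day window as one unit, with l = -ln(1-b) and m = -ln(1-d). The share readmitted before death is l/(l+m) × (1 - exp(-(l+m))).

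- b = 0.25, so l = 0.2877. With d = 0.05, m = 0.0513 and the share is 0.2877/0.3390 × 0.2875 = 24.4%. With d = 0.10, m = 0.1054 and the share is 0.2877/0.3930 × 0.3250 = 23.8%. The difference is 0.61 points.
- b = 0.30 gives 29.3% against 28.6%, a difference of 0.73 points.

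The standard error is sqrt([p1(1-p1) + p2(1-p2)]/176), which is 4.56 points for b = 0.25 and 4.83 for b = 0.30. The z values are 0.13 and 0.15.

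**Frailer patients more prone to both events.** A shared lognormal frailty (SD 1) multiplies both hazards, recalibrated to the same b and d. The results are 24.0% against 23.1% (0.99 points, z 0.22) and 29.0% against 27.9% (1.09 points, z 0.23).

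**All deaths before discharge.** With everyone randomised as the base, the shares are b × 0.95 and b × 0.90: 23.75% against 22.5% (1.25 points, z 0.28), or 28.5% against 27.0% (1.5 points, z 0.31). With patients discharged alive as the base, the difference is zero.

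**Effect on the test.** At the largest shift, z = 0.31, a two-sided 5% test would reject with probability P(Z > 1.65) + P(Z < -2.27) = about 6.1%.

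**Equal mortality.** The distortion between arms is zero. The percentage within each arm does move with the base. For b = 25%, 5% dying in hospital and 20% dying after discharge, it is 21.4% of those randomised, 22.5% of those discharged alive and 25.0% of those alive at Day 30. The shift is the same in both arms.

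**Can the facts be obtained under the plan as written?**

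- Discharge date: T3 cannot be scheduled without it, and the index stay is in the participating hospital.
- Death: the caregiver is due to be questioned at T3, and the linkage log holds telephone numbers. A caregiver reached at T3 would be expected to report a death, so a missing patient form or a reported death is likelier than an unexplained zero.
- Other fields: the data collection sheet gives headings rather than form fields, and Section XII allows for further instruments.

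**The case for a change.** The strongest case for a change is that knowing a date is not the same as recording it for analysis. A hospital chart may miss a death at home, and no text says that the T3 interview goes ahead with the caregiver once the patient has died. An analysis limited to patients alive at T3 would drop real events. Under the same assumed models it omits about 3-6% of readmitted patients when 5% die, 5-11% when 10% die and 11-21% when 20% die. Date fields and a sentence or two in Section XI would be cheap. There is also a small inconsistency over who records the data: Section IX says "The BSC will collect all data following patient randomization", while Section XII has the other coordinator (CSC) complete the sheet that holds readmissions.

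Most of this is factually right. The text is silent, and a careful team would name the dates on its forms and settle the base before looking at results. But the plan sets no rule that yields a wrong answer; in particular, it does not restrict the analysis to survivors. Nor is there one obvious rule to add. The set discharged alive is defined after randomisation, and counting events up to death within it leaves the 0.6 to 1.1 point effect of post-discharge deaths in place. Reporting deaths by arm beside the outcome would make that effect visible, and the analysts can do so without a prior change to the plan. The lack of outcome models in Section XI applies to every endpoint and is a separate matter.

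**Conclusion.** No change follows. The denominator, the handling of death and the date fields are unwritten, but the schedule depends on the discharge date, a caregiver is due to be questioned at Day 30, and further instruments are provided for. Under no treatment effect on readmission, the distortion is zero if mortality is equal. It is 0.6 to 1.5 points (z 0.13 to 0.31) if mortality is 5% against 10% and 25-30% would otherwise be readmitted. Against a standard error of 4.5 to 4.8 points, that would not by itself produce a significant result. The size rests on assumed rates, because the documents give none, and a much larger mortality difference between arms would raise it. The conclusion also rests on sites learning of deaths through the caregiver or the chart, which the plan makes likely but does not guarantee. This is a minor completeness point on one secondary outcome.

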## **III. Study Population**

The hospitals chosen for this study represent typical rural hospitals in size and population representativeness of many of the underserved facilities in the Deep South.

- a. Russell Medical Center, Alexander City, AL:** Russell Medical Center is a not-for-profit, acute care facility serving the needs of east Central Alabama. It is a general medical and surgical hospital in Alexander City, AL, with 80 beds. Survey data for the latest year available shows that 24,827 patients visited the hospital's emergency room. There are 67 physicians affiliated with the hospital, and the hospital had a total of 3,245 admissions. Its physicians performed 835 inpatient and 3,264 outpatient surgeries. Russell Medical Center also expounds upon community health education services through health screenings, support groups, childbirth classes, self-help programs, and athletic trainers to multiple sports teams in its service area.
- b. Highland Community Hospital, Picayune, MS:** Highland Community Hospital is a 60-bed not-for-profit hospital and affiliated clinics provide access to a broad range of quality services, supporting the community and enhancing the level of care for the residents of Picayune MS and the surrounding areas. There are 100 physicians affiliated with the Highland Community Hospital. Its community outreach includes classes and events in different themes including community education, continuing education, screenings, support groups etc.
- c. Aiken Regional Hospital, Aiken, SC:** Aiken Regional Medical Centers, located in Aiken, South Carolina, is a 245-bed acute care facility offering a comprehensive range of specialties and services. The medical staff includes over 900 skilled healthcare/support professionals, a medical staff of more than 120 multi-specialty physicians, and a team of 230 volunteers. The center provides nearly 50 specialty services through its acute care facility, behavioral healthcare hospital and the cancer care institutes of Carolina. Its services reached in Aiken and its surrounding communities. There are different types of the community outreach in Aiken Regional Medical center, including classes, seminars, support groups, or information about new services.

#### IV. Study Design

This study consists of 2 phases:

**Phase I Convening & Soliciting CAG Participation in study design.** This phase will consist of assembling CAG members to review study procedures and some CAG members will be trained to approach potential study participants. Potential CAG members (8, with equal numbers of AA and W) will be identified by the hospital staff and community leaders of each of the three sites, and invited to participate in the CAG. Potential CAG members will include respected members of the community, those who have recently lost a loved one and understand end of life care, and community leaders. Potential members will be discussed by the recruiters with the study PIs to ensure there is socio-demographic balance, and equal representation of African American and

White members, to ensure all will feel comfortable participating and contributing, and to ensure that they are not all from the same family/church/social group. Following this step, a formal written invitation will be extended to those selected, followed by a phone call by the Study Manager.

**Phase II Conducting the RCT.** In Phase II, we will conduct a randomized controlled trial (RCT) at the 3 sites to test the effectiveness of this innovative program. We will recruit 352 hospitalized AA and W adults over age 65 whose treating physician would not be surprised if they died within the next year and the patients' family/friend caregiver. Half of the patient participants (N=176) will be randomized to receive usual care appropriate to their illness. Patients randomized to usual care in each of the three participating hospitals will receive inpatient care appropriate to their illness. This includes assessment and treatment by the admitting physician, along with any subspecialists that are consulted. The formulation and sharing of prognostic information and the engagement of patients and families in establishing goals of care will be according to the standards of the admitting physician and subspecialists. Treating clinicians may include hospitalists, nurse practitioners, social workers, pastoral care, and occasionally, the patient's primary care practitioners who have hospital privileges.

The other half of the patient participants (N=176) will receive the culturally-based palliative care consult. Patients in the intervention group will receive usual care as described above, and, in addition, will participate in a standardized, comprehensive palliative care Tele-consult

assessment as well as a follow up by the palliative care physician on Day 3 and 6 following the initial consult.

